### 4.13.3 Immunogenicity

The immunogenicity of CBP-201 with prolonged use will be determined with the collection of blood samples for measurement of anti CBP-201 antibodies (ADA) throughout the study. Further, neutralizing activity of neutralizing antibodies (NAb) will be measured on samples that test positive for anti CBP-201 antibodies. Absolute analysis value and change from baseline of ADA and NAb blood sample will be summarized by treatment using descriptive statistics on PK Set. By-subject listing will also be provided.

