- i. All women of childbearing potential will be tested for pregnancy by a serum pregnancy test at Screening and by urine pregnancy tests at Baseline and thereafter. A negative result must be obtained prior to randomization.
- j. A patient diary and NPIF meter will be issued to the patient with training at Screening visit. At all study visits, patients should be assessed for compliance and retrained, if necessary, on the use of the patient diary device and NPIF meter.
- k. A questionnaire of Health Care Resource Utilization. For more details see section 7.8.12.
- l. Serum chemistry panel: sodium, potassium, chloride, bicarbonate, creatinine, blood urea nitrogen, glucose, calcium, uric acid, total protein, total bilirubin, albumin, alanine aminotransferase, aspartate aminotransferase, alkaline phosphatase, lactate dehydrogenase, gamma-glutamyltransferase, creatine phosphokinase, total cholesterol, triglycerides, and C-reactive protein. The blood sample must be taken with the patient in fasting state which means no intake of any food or drink except for water for at least 8 hours.
- m. Hematology: hemoglobin, hematocrit, platelet count, total white blood cell count with 5-part differential count, differential count, and total red blood cell count.
- n. PK blood samples should be collected prior to dosing; date and clock time for each sample should be recorded.
- o. PD blood samples for biomarkers of inflammation include Eotaxin-3, eosinophil cationic protein, total immunoglobulin E, thymus and activation-regulated chemokine, and periostin. Blood eosinophil count will be measured as part of hematology test. C-reactive protein will be determined as part of the serum chemistry.
- p. ADA blood sample: NAb will be tested at all ADA collection time points in samples that are ADA positive.
- q. Patients are to be observed for 2 hours postdose on D1 (V2), W2 (V4), and W4 (V5), and 30 minutes postdose for W6 (V6) and beyond. Assessments and testing should be completed predose except as noted otherwise. Rotate injection sites: abdomen (avoid area proximal to umbilicus), outer thigh, and upper arm (lateral or posterolateral). Only 1 mL should be injected per site, and an injection site should not be in the same anatomical location used during the previous visit.

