### 4.2 Definitions

#### Age at Baseline

Age will be calculated using the date of birth and date of the baseline visit as below:

Integer part of [(Date of Baseline Visit – Date of Birth) / 365.25]

Baseline

Unless otherwise specified, baseline is defined as the last non-missing value prior to the first dose of study drug. If time is not collected but the assessment is performed on the same day as the first dose of study drug, it would be considered as baseline.

Baseline Week

For weekly average analysis, baseline week is defined as 7 days prior to the baseline visit (Study day ranges from -7 to -1).

Change from Baseline

Change from baseline is defined as post-baseline value minus baseline value.

Study Day 1

Study day 1 is defined as the date of randomization for untreated randomized subjects or the date of first dose for treated subjects.

Study Day

Study Day will be calculated relative to the date of randomization for untreated randomized subjects and relative to the date of first dose for treated subjects.

If event is prior to the first dose, then study day is calculated as:

$$\text{Date of Event} - \text{Date of First Dose}$$

If event is after the first dose, then study day is calculated as:

$$\text{Date of Event} - \text{Date of First Dose} + 1$$

Duration of Treatment

Duration of Treatment (days) will be calculated as:

$$\text{Last Date of Dose} - \text{First Date of Dose} + 1$$

Treatment-Emergent Adverse Events

Treatment-emergent adverse events are defined as any adverse events occurred or worsen during the treatment-period, whether considered related to the treatment.

Where the AE start date is missing, adverse events will be assumed to be treatment-emergent, unless there is clear evidence (through comparison of partial dates) to suggest that the adverse event started prior to the first dose of study treatment.

Prior and Concomitant Medication

Prior and concomitant medication is defined as any medications that started before the first dose of study drug and stops on or after the first dose of study drug.

Prior Medication

Prior medication is defined as any medications that started and stopped before the first dose of study drug.

Concomitant Medication

Concomitant medication is defined as any medications that started on or after the first dose of study drug.

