## 4.3 General Presentation Considerations

Continuous data that are assumed to be normally distributed will be summarized in terms of the mean, standard deviation (SD), median, minimum, maximum and number of observations. Continuous data that are expected to be skewed will be presented in terms of the maximum, upper quartile, median, lower quartile, minimum and number of observations. The minimum and maximum will be reported to the same number of decimal places as the raw data recorded in the database. The mean, median, lower quartile and upper quartile will be reported to one more decimal place, and the SD (and the standard error [SE], if applicable) will be reported to two more decimal places, than the raw data recorded in the database. In general, the maximum number of decimal places reported shall be four for any summary statistic.

Categorical data will be summarized in terms of the number of subjects providing data at the relevant time point (n), frequency counts and percentages. Any planned collapsing of categories will be detailed in the SAP text and the data displays.

Percentages will be presented to one decimal place except 100%. 100% will be presented as 100% instead of 100.0%. Percentages will not be presented for zero counts. Percentages will be calculated using the number of subjects (n) as the denominator. If sample sizes are small, the data displays will show the percentages, but any textual report will describe frequencies only. A missing category shall be included only for categorical variables where no data is available. The missing category will be omitted if there were no missing values for that variable.

Changes from baseline in categorical data will be summarized using shift tables where appropriate.

Laboratory values contain ‘ $\geq x$ ’ or ‘ $x \leq$ ’ will be taken as the value of x in the analysis. If a laboratory value contains ‘ $y <$ ’ then y minus 0.001 will be used for the analysis. If a laboratory value contains ‘ $z >$ ’ then z plus 0.001 will be used for the analysis.

P-values greater than or equal to 0.001, in general, will be presented to three decimal places. P-values less than 0.001 will be presented as “ $<0.001$ ”. P-values greater than 0.999 will be presented as “ $>0.999$ ”.

Confidence intervals will be presented to one more decimal place than the raw data.

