#### Safety Set (SS)

The Safety Set (SS) is defined as all randomly assigned patients who received at least 1 dose of study treatment. These patients will be categorized according to the treatment they actually received. If a subject is allocated the incorrect study treatment as per the study randomization list, subjects will be summarized and analyzed 'as treated' i.e. by allocated treatment group. The safety summaries and analyses will be based on the Safety Set.

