#### Pharmacokinetic Set (PKS)

The Pharmacokinetic Set (PKS) consists of all randomly assigned patients from whom at least 1 post-dose PK blood sample was collected. Pharmacodynamic (PD) and/or PK relationships will be explored in a separate analysis plan and report.

An analysis population classification meeting will be arranged to discuss the outputs and to decide which subjects and/or subject data will be excluded from certain analyses. Decisions made regarding the exclusion of subjects and/or subject data from analyses will be made prior to unblinding and will be documented and approved by Suzhou Connect Biopharmaceutical Ltd.

The number and percentage of subjects in each analysis set by treatment group and overall will be summarized on Randomised Set. By-subject listing of analysis population assignment will also be provided.

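### The planned change-from-baseline summary of neutralising antibodies is undefined for every patient who converts on treatment, and no table gives the per-patient incidence of treatment-emergent antidrug antibodies by arm

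*SAP*

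**What the plan says.** SAP 4.13.3 states the analysis in one sentence: "Absolute analysis value and change from baseline of ADA and NAb blood sample will be summarized by treatment using descriptive statistics on PK Set". It adds a by-subject listing. The same section limits the neutralising assay: "neutralizing activity of neutralizing antibodies (NAb) will be measured on samples that test positive for anti CBP-201 antibodies". Footnote p of the schedule in SAP 3.2 agrees: "NAb will be tested at all ADA collection time points in samples that are ADA positive". The protocol's schedule carries the same footnote.

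SAP 4.2 supplies the definitions that the summary relies on. By default, "baseline is defined as the last non-missing value prior to the first dose of study drug", and "Change from baseline is defined as post-baseline value minus baseline value". SAP 4.3 adds a general rule: "Changes from baseline in categorical data will be summarized using shift tables where appropriate".

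On population, ADA and NAb are among the safety endpoints in protocol 3.9.6 and SAP 3.3.1.6. Protocol 9.2 assigns safety endpoints to the Safety Set, and SAP 4.6 says: "The safety summaries and analyses will be based on the Safety Set". SAP 4.13.3 uses the PK Set instead, which "consists of all randomly assigned patients from whom at least 1 post-dose PK blood sample was collected".

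Protocol 9.6 asks for ADA and NAb by treatment group and scheduled visit, and its next sentence, on change from baseline, treats them as continuous parameters.

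**The concern.** The sentence in SAP 4.13.3 follows the wording that SAP 4.13.2 uses for continuous biomarkers such as IgE and periostin. The documents otherwise describe ADA samples as positive or not, and that status decides whether NAb is measured at all. Neither document mentions a titre, defines treatment-emergent ADA, or says how an ADA-negative sample is coded for NAb.

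The basic immunogenicity result for two active regimens is how many patients in each arm developed antibodies, and how many of those antibodies were neutralising. SAP 4.15 now directs the terminated trial's analyses towards safety, and it leaves this summary in place. If the table is programmed as written, the NAb change columns will hold no converters, and the ADA result will need someone to count patients with no prespecified definition or denominator.

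**Working it through.** The plan gives no figure to reproduce here. The check is one of definitions, visit schedules and counting.

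**1. Who can have a NAb change from baseline?** The change is NAb(post) minus NAb(baseline), so both results must exist, and each exists only if that sample was ADA-positive.

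| ADA at baseline | ADA later | Baseline NAb | Later NAb | NAb change |
|---|---|---|---|---|
| negative | negative | none | none | undefined |
| negative | positive (converter) | none | measured | undefined |
| positive | negative | measured | none | undefined |
| positive | positive | measured | measured | defined |

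Taking the last non-missing pre-dose value does not help. ADA is first drawn at Visit 2 (protocol Table 1 and section 6.2), so there is no earlier sample to fall back on. No rule sets an unassayed NAb to negative. Converters in the NAb change summary: 0, whatever the conversion rate.

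**2. Scale, under assumed rates.** The documents give no ADA rate and no final enrolment. Assume that no patient is ADA-positive at baseline and that a proportion t converts. Expected converters per arm are N × t, and the chance of at least one is 1 − (1 − t)^N.

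| N per arm | t | Expected converters | Chance of at least one | In NAb change summary |
|---|---|---|---|---|
| 49 (planned) | 2% | 0.98 | 63% | 0 |
| 49 | 5% | 2.45 | 92% | 0 |
| 49 | 10% | 4.9 | 99% | 0 |
| 20 (assumed, after early termination) | 2% | 0.4 | 33% | 0 |
| 20 | 5% | 1.0 | 64% | 0 |
| 20 | 10% | 2.0 | 88% | 0 |

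**3. Can by-visit tables give the incidence?** There are four scheduled post-dose ADA draws: Visits 5, 9, 15 and 17. A by-visit shift table gives a count at each. The number of patients who were ever positive lies between the largest of the four counts and their sum (capped at the number of patients). If each visit showed one negative-to-positive shift, the number of converters could be anything from 1 to 4. The tables alone cannot settle it; the listing can, but only by hand counting.

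**4. Does the PK Set lose patients?** From protocol Table 1 and section 6, with totals matching protocol Table 3:

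- ADA draws (5): Visits 2, 5, 9, 15, 17.
- PK draws (7): Visits 2, 3, 5, 9, 15, 16, 17.

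Every ADA visit is also a PK visit, and both samples are taken at early termination. A patient with a post-dose ADA result falls outside the PK Set only if every post-dose PK sample was missed.

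**The case against.** The best defence is that the SAP does not say mean change. It says descriptive statistics, and SAP 4.13.4 uses the same phrase for a categorical item, surgery for nasal polyps. If ADA is reported as positive or negative, SAP 4.3 would give counts and percentages by arm and, where judged appropriate, shift tables that show negative-to-positive moves. The listing shows each patient's results, and with few patients a listing is quite workable.

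Much of this stands, and it rules out two stronger readings. A reader might infer that the plan cannot show treatment-emergent immunogenicity at all. The documents do not support that: shift tables and the listing can both reveal conversions. A reader might also infer that patients who develop antibodies are excluded from the analysis. That is true only of the NAb change summary. Converters stay in the NAb absolute values and the listing, and the PK Set has no antibody condition. Whether they stay in the ADA change summary depends on how negative samples are coded, which is not stated. For the same reason one cannot say outright that a change in ADA is meaningless: the reporting scale is not given.

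The defence does not reach the NAb change column, which fails by the SAP's own definitions. Nor does it supply a per-patient incidence, because by-visit counts cannot be combined without patient-level data and the listing comes with no definition or denominator.

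**Conclusion.** The point holds as a gap in specification with one firm defect. The firm defect is that the NAb change from baseline is undefined for every converter, so none can contribute. This rests only on the ADA-positive testing rule, the SAP's definition of change, and the absence of a coding rule for unassayed samples. The gap is that no planned summary gives treatment-emergent ADA incidence per patient by arm. How many patients are affected is unknown, and the rates in the working are assumptions for scale only.

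The use of the PK Set contradicts protocol 9.2 and SAP 4.6, and SAP 4.15 does not list it as a change. Its numerical effect is probably small, because PK is sampled at every ADA visit. It should be reconciled, but it is not a reason to think that antibody-positive patients are being dropped. The change is worth making because immunogenicity is among the safety results on which the terminated trial will now report.

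**What to change.** In SAP 4.13.3, replace the change-from-baseline summary with one table by arm, among Safety Set patients who have a baseline and at least one post-baseline ADA result:

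- ADA-positive at baseline, n (%).
- Treatment-emergent ADA, n (%) with exact 95% CI, defined as negative at baseline and positive at any later sample, plus boosted titre in patients positive at baseline if titres are reported.
- NAb-positive, n (%), with ADA-negative samples counted as NAb-negative, shown both over all ADA-evaluable patients and over ADA-positive patients, with each denominator stated.

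Summarise titre only if the laboratory reports it. Keep the by-subject listing, and keep by-visit counts of status to meet protocol 9.6. State which analysis set applies and why, and record the change in SAP 4.15. The evaluable condition matters: the whole Safety Set as denominator would include dosed patients with no post-baseline ADA sample and so dilute the incidence.

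The cost is one paragraph and one table shell. All the data are already being collected.

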### 4.13.4 Health Economics

The following data will be collected during the study in health care utilization eCRF:

- Number of visits (in-person or telehealth) to usual healthcare provider for nasal polyps since last visit
- Number of urgent care admissions for nasal polyps since last visit
- Number of emergency room admissions for nasal polyps since last visit
- Number of days on hospitalization for nasal polyps since last visit
- Incident of surgery for nasal polyps since last visit

Each question at each visit will be summarized by treatment and overall using descriptive statistics. By-subject listing of health care utilization will also be provided.

## 4.14 Determination of Sample Size

The sample size of the study is determined based on the comparison between CBP-201 300 mg every 2 weeks vs. placebo with regard to the co-primary endpoint change from baseline in NPS at Week 24 (LIBERTY SINUS studies, Bachert et al 2019). Assuming a common standard deviation in the NPS of 2.1, and based on the use of a two-sided test at the alpha=0.05 level of significance 41 patients per

group will provide 80% power to detect a difference of 1.3 between the CBP-201 group and the placebo group in the change of NPS from baseline to Week 24. To allow for a 15% dropout rate, the planned samples size is 49 subjects per group (147 total).

- Roughly, to ensure at least 74 patients have co-morbid asthma: Recruitment of NP patient without co-morbid asthma will stop when approximately 70 patients without asthma are randomized, and
- Patients with co-morbid asthma will continue to be randomized to complete a total number of 147 randomized NP patients.

If greater than 15% of the treated patients do not complete the study, the sample size may be adjusted to ensure adequate power.

#### **4.15 Changes in the Conduct of the Study or Planned Analysis**

Enrollment of Sponsor's Phase 2 trial evaluating CBP-201 in chronic rhinosinusitis with nasal polyps, which commenced in June 2021, has faced challenges due to the macroenvironment -- namely ongoing impact of COVID and the current Russia-Ukraine conflict throughout [Eastern] Europe.

Therefore, the Sponsor has made the decision to terminate this trial early, and the planned analyses have been changed to focus on safety assessments.

For the efficacy endpoints, only descriptive summary statistics will be provided for the co-primary efficacy assessments. No formal hypotheses will be tested due to the small sample size. No sensitivity or subgroup analyses will be performed. All other efficacy assessments will be listed except percentage of maxillary sinus volume occupied by disease on CT and Lund-Mackay Computed Tomography scores.

## 6 APPENDICES

### 6.1 Appendix A – Visual Analogue Scale for Rhinosinusitis (VAS-RS)

**Seriousness of the complaints:** Please draw a vertical line to the point that best corresponds to, how bothersome were the following symptoms within the last month, as given to the example:

\* Example      None      More than I can imagine

---

\* Total sinus symptoms:

None      More than I can imagine

---

\* Nasal blockage:      None      More than I can imagine

---

\* Headache /pressure on the face:

None      More than I can imagine

---

\* Loss of smell:      None      More than I can imagine

---

\* Post-nasal drip (secretions from the nose down to the throat):

None      More than I can imagine

---

\* Runny nose:      None      More than I can imagine

---

\* Itchy eyes:      None      More than I can imagine

# Parexel International

Suzhou Connect Biopharmaceuticals Ltd.  
CBP-201-WW003

Statistical Analysis Plan

---

\* Itchy nose:      None      More than I can imagine

---

\* Sneezing:      None      More than I can imagine

---

\* Tearing:      None      More than I can imagine

---

\* Cough:      None      More than I can imagine

---

\* Tightness/pressing sensation on the chest:

None      More than I can imagine

---

\* Shortness of breath/difficulty with breathing:

None      More than I can imagine

---

\* Wheezing:

None      More than I can imagine

---

## 6.2 Appendix B – Total Nasal Symptom Score (TNSS)

Total Nasal Symptom Scores (TNSS) is the total of 4 related symptoms. Each symptom (sneezing, congestion, itching, and rhinorrhea) is graded from 0 to 3 by the patients.

Score	Description	Symptoms
0	None	No symptoms evident
1	Mild	Symptom present but easily tolerated
2	Moderate	Definite awareness of symptom; bothersome but tolerable
3	Severe	Symptom hard to tolerate; interferes with daily activity

The nasal symptoms are then added together for each symptom to get the total TNSS.

## 6.3 Appendix C – Sino-Nasal Outcome Test-22 QUESTIONNAIRE (SNOT-22)

Figure S1: Sino-Nasal Outcome Test-22 Questionnaire

A: Considering how severe the problem is when you experience it and how frequently it happens, please rate each item below on how 'bad' it is by circling the number that corresponds with how you feel using this scale →		No problem	Very mild problem	Mild or slight problem	Moderate problem	Severe problem	Problem as bad as it can be	
1. Need to blow nose		0	1	2	3	4	5	
2. Sneezing		0	1	2	3	4	5	
3. Runny nose		0	1	2	3	4	5	
4. Cough		0	1	2	3	4	5	
5. Post nasal discharge (dripping at the back of your nose)		0	1	2	3	4	5	
6. Thick nasal discharge		0	1	2	3	4	5	
7. Ear fullness		0	1	2	3	4	5	
8. Dizziness		0	1	2	3	4	5	
9. Ear pain		0	1	2	3	4	5	
10. Facial pain/pressure		0	1	2	3	4	5	
11. Difficulty falling asleep		0	1	2	3	4	5	
12. Waking up at night		0	1	2	3	4	5	
13. Lack of a good night's sleep		0	1	2	3	4	5	
14. Waking up tired		0	1	2	3	4	5	
15. Fatigue		0	1	2	3	4	5	
16. Reduced productivity		0	1	2	3	4	5	
17. Reduced concentration		0	1	2	3	4	5	
18. Frustrated/restless/irritable		0	1	2	3	4	5	
19. Sad		0	1	2	3	4	5	
20. Embarrassed		0	1	2	3	4	5	
21. Sense of taste/smell		0	1	2	3	4	5	
22. Blockage/congestion of nose		0	1	2	3	4	5	

TOTAL: \_\_\_\_\_

GRAND TOTAL:

\_\_\_\_\_ Copyright Washington University

## 6.4 Appendix D – Laboratory SI Units

Panel	Parameter	SI Unit
Hematology	Eosinophil Count	10  /L
	Hematocrit	Proportion of 1.0
	Hemoglobin	g/L
	Platelet Count	10  /L
	Red Blood Cell (RBC) Count	10  /L
	White Blood Cell (WBC) Count with Differential	%
Serum Chemistry	Alanine Aminotransferase (ALT)	U/L
	Albumin	g/L
	Alkaline Phosphatase (ALP)	U/L
	Aspartate Aminotransferase (AST)	U/L
	Blood Urea Nitrogen (BUN)	mmol/L
	Calcium	mmol/L
	Bicarbonate	mmol/L
	Chloride	mmol/L
	Creatinine	µmol/L
	Creatine Phosphokinase (CPK)	U/L
	C-Reactive Protein (CRP)	mg/L
	Gamma-Glutamyltransferase (GGT)	U/L
	Glucose	mmol/L
	Lactate Dehydrogenase (LDH)	U/L
	Potassium	mmol/L
	Sodium	mmol/L
	Total Bilirubin	µmol/L
Urinalysis	Total Cholesterol	mmol/L
	Total Protein	g/L
	Triglycerides	mmol/L
	Uric Acid	mmol/L
	Bilirubin	NA
	Hemoglobin	NA
	Glucose	NA
	Ketones	NA
	Leukocytes	NA

